Session 2: (TELEVIDEO) Session 2 is conducted via televideo directly into the participant's home and begins with a review of homework and verbal reinforcement of completed daily assessment monitoring forms, restatement of the rationale, and problem solving. Next, the five values areas are discussed (relationships, vocation, recreation, physical/spiritual, and responsibilities) and specific values under these categories generated and listed. These are then used to derive highly specific behaviors that illustrate these values, and these specific, values-consistent behaviors are placed on the Values and Activities form. Behaviors are classified as either positively reinforcing (i.e., enjoyable behaviors), negatively reinforcing (e.g., behaviors such as chores that, when completed, result in reduction of stress or aversiveness), or exposure-based, such as behaviors that are incompatible with bereavement-related avoidance (e.g., looking at photos of the deceased, going to a military-focused event). Each reinforcing behavior is rated from 0 - 10 in terms of its reinforcing potential as well as its difficulty to complete. Whenever possible, behaviors are framed in a social context. It is at this point that the daily monitoring form the patient used in the first session is translated into a daily planning form. Thus, participants are instructed to

select activities that they have just generated from the Values and Activities form, and use them to plan events for the remainder of the current day, and the next two days, with the objective of at least 3 hours of reinforcing activities and 30 minutes of exposure behaviors planned each day. Participants are instructed to plan ahead to the next day, and keep ahead one day.

A discussion of the bereaved and how they are currently playing a part in the patient's life is also initiated. The concept of exposure to these memories and thoughts as a way of honoring those who did not make it home, not simply as a way to become desensitized to these memories, is reviewed. We frame the grief processing in this way because we have noted that many bereaved individuals state that they do not want to 'heal' and that they equate lessening of negative affect related to the loss of their comrade with 'forgetting' him or her. We are very careful to validate feelings of loss and assure patients that 'getting better' is not the same as 'forgetting', with focus placed on what their friend would have wanted for them, which is probably good memories, rather than painful memories. Thus, as an exposure exercise the therapist and patient review in extensive detail the thoughts and feelings experienced with respect to the bereaved. This also helps to identify any actual behavioral avoidance (e.g., military events) that may be taking place and these are also addressed.

Session 3: (TELEVIDEO) These sessions begin with a review of homework, followed by asking the participant to state, in their own words, their interpretation of the rationale for Behavioral Activation and Therapeutic Exposure. Obstacles to completing scheduled behaviors are discussed and additional exposure based and reinforcing behaviors are generated, consistent with participant values, and placed on the Values and Activities form. The need to constantly update this form is stressed, and therapists illustrate that this form should be used in conjunction with the daily planner so that planning is easier, and values-consistent. If a participant failed to use the planner, therapists address the difference between planning for a good day and 'hoping' for a good day, comparing this to planning for effective combat based on training and hard work vs. "hoping" for successful combat outcomes based on only hope. Behaviors that were consistently planned on the daily planner but not completed are removed and alternative behaviors suggested. A discussion of avoidance behaviors related to bereavement is held, and exposure activities derived from this are added to the list. The next day's activities are planned. Following the behaviorally focused work, the discussion / processing of bereavement related memories and feelings is reviewed, with a focus on the events up to and including the death of the friend, and the ensuing days and months. Again, the major emphasis is on exposure to, rather than avoidance of these cognitions and feelings. The next 2 days of activities are planned.

Sessions 4, 5, and 6: (TELEVIDEO) Homework is reviewed with an emphasis on reinforcing the participant for following the daily planner. Values and Activities lists are expanded, as is the list of avoided behaviors. Each behavior that was planned but not completed is addressed, and those that are consistently planned but not completed are removed from the planner. Each session is focused on problem solving and implementing both planning, and execution of planned, exposure-oriented activities. The last half of each session is again devoted to an in depth discussion of the bereaved and

processing the thoughts and feelings associated with this discussion. At the end of each session, the next 2 days of activities are planned as per above.

Session 7: (OFFICE-BASED) The final session includes discussion of the rationale and treatment gains obtained thus far. Discussion is also centered on the need to continue planning activities and using a daily planner for at least 6 months. Relapse prevention strategies are reviewed.

Comparison Condition: Cognitive Restructuring and Supportive Grief Counseling as Outlined by the VA/DoD Iraq War Clinician Guide (Chapter 11): The primary purpose of this condition is to serve as a 'current standard of care' comparison control condition, matched to the experimental condition in both duration and modality of treatment delivery. Therefore, specific components of the Experimental treatment, such as focused and specific activity scheduling will not be present. The same counselors will deliver this treatment according to the same schedule of in person and televideo sessions as the experimental intervention (1 in person, followed by 5 televideo, followed by a final in person).

As with BATE-G, sessions will be conducted once per week for 75 minutes. The VA's National Center for PTSD Iraq War Clinician Guide, 2nd ed. offers the following summary (Pivar, 2007) of treatment for traumatic grief, which overlays highly with standard supportive grief counseling. The Guide Summarizes:

"There have been no outcome studies of treatments of veterans for prolonged and complicated grief symptoms at this time. Clinical experience supports the importance of education about normal and complicated grief processes, education about the cognitive processes of guilt, restructuring of cognitive distortions of events that might lead to excessive guilt, looking at the function of anger in bereavement, restoring positive memories of the deceased, restoration and acknowledgment of caring feelings towards the deceased, affirming resilience and positive coping, retelling the story of the death, and learning to tolerate painful feelings as part of the grieving process. Regardless of the techniques that are used, what is central to treating veterans for prolonged and complicated grief is recognition of the significance of their losses, provision of an opportunity to talk about the deceased, restructuring distorted thoughts of guilt, and validation of the pain and intensity of their feelings."

Session 1: (OFFICE-BASED) The first session will involve review of the Veteran's loss, and recognition that the loss was significant, enduring and painful. In addition, education about normal vs. problematic grief reactions will be discussed. The parameters of the loss, its meaning and its current impact will be explored. A discussion of positive memories of the deceased will be initiated and the Veteran will determine the course of this discussion.

Session 2: (TELEVIDEO) The second session will focus on a review of points raised in the first session, followed by further discussion of cognitive processes of guilt often associated with bereavement. Positive memories of the lost comrade will be explored, and the meaning of guilt in the context of these positive images outlined and discussed.

Sessions 3-6: (TELEVIDEO) The third through sixth sessions will review points raised in the prior session, and then address the function of anger in bereavement. This is often a sensitive, guilt-facilitating issue, and sufficient time will be afforded to process these conflicting feelings of guilt, loss, longing and anger. Again, the concept of restoring positive memories about the deceased, a common thread across these sessions, will be raised. Discussion of the story of the

death will take place, with attention directed to specific cognitive distortions in the context of the aforementioned conflicting emotions addressed.

Session 7: (OFFICE-BASED) will focus on restoring positive memories of the deceased, focusing on the concept of tolerating painful or mixed feelings in the context of these memories. In addition, integration of 'lessons learned' from prior sessions regarding guilt, anger, sadness, and also positive emotions attached to the memory of the lost comrade will be reviewed.

Treatment Integrity and Training. Counselors will receive the video and brief treatment manual and will be asked to review these prior to a 4-hour training with the study PI. At this training, the study PI will go over key points of the intervention outlined above. A key treatment tool, the video, has been specifically designed as a treatment training mechanism in itself. In addition, all treatment sessions will be audio taped and 20% of case tapes will be reviewed for treatment integrity by two trained independent raters according to session checklists. In this way, we will assure that directive treatment procedures found in the BATE-G condition are not delivered in Cognitive Restructuring and Supportive Grief Counseling.

Treatment Providers. Treatment providers will be master's level counselors with at least 2 years of experience providing bereavement counseling to adults. All providers will perform both treatments.

HIPAA Compliance for Home-Based Televideo Equipment. In order to assure patient Confidentiality and HIPAA compliance, we will use the MUSC/Charleston VAMC contracted version of HIPAA compliant software for televideo patient care. If participants do not have a computer, we will supply them with a tablet for use during the study, as we have done with our two ongoing telemedicine treatment studies with Veterans.

Dependent Measures & Interviewers. All measures will be administered by master's level research assistants who are blind to experimental condition and who achieve interrater reliability on 5 practice assessments of 90%. All participants in both conditions will complete most measures at pre-treatment/baseline (at least 6 months post-death), post-treatment, and 3 & 6 months post-treatment. The timing of assessments with study procedures is described in the diagram below. In pilot testing of the assessment battery, 42 minutes was the average time of completion for self report, with another 30-40 minutes necessary for the selected modules of the Structured Clinical Interview for DSM 5.

DOMAIN	MEASURE	DESCRIPTION	TIMING
Demographics	Race Gender etc.	Descriptive self-report	Baseline
Prolonged Grief Disorder	Inventory of Complicated Grief, Revised (Prigerson, et al, 2001)	34item self-report; total intensity score; high reliability, concurrent validity with BDI & satisfactory criterion validity (Prigerson et al., 1995; 1997; Silverman et al., 2000; 2001)	Base, Post-Tx, 3 & 6 month
Selected Axis I Mental Diagnoses	Structured Clinical Interview for DSM-5 (To Be released)	Clinician administered, gold standard; Dx: Major Depression, Panic Disorder, Generalized Anxiety Disorder, PTSD, Sub. Use Disorder. (Last version TBA)	Base, Post-Tx, 3 & 6 month

Depression	Beck Dep Inventory-II (Beck et al, 1996)	21 item self-report; high reliability and concurrent validity (Beck, Steer, & Brown, 1996)	Base, Post-Tx, 3 & 6 month
PTSD	PTSD Symptom Scale (Foa et al., 1993)	17 item self-report; 3 subscales. High reliability and concurrent validity (Foa et al., 1993)	Baseline, Post-Tx 3 & 6 month

Power Analysis. The primary longitudinal efficacy outcome variables are: intensity of PGD symptoms (ICG), and depression symptom severity (BDI) and PTSD (PCL) variables. In several studies of behavioral activation for mood disorders by Lejuez and colleagues (Hopko, Lejuez, & Hopko, 2004; Hopko et al., 2003; Lejuez et al., 2011, Lejuez, Hopko, & Hopko, 2001; MacPherson et al., 2010), effect sizes of .7 to 1.5 were obtained. In addition to behavioral activation, the present intervention also includes a video-based treatment for PTSD-like symptoms of complicated bereavement based on our existing treatment for PTSD in combat Veterans. In the pilot study, this treatment achieved an effect size of 0.7 on psychological outcomes, and .25-.3 on health outcomes. For comparing the longitudinal profile of continuous outcomes for the BATE-G versus Comparator groups across the study period [assuming 4 measurement time points, level of significance alpha=0.05, two-tailed comparison, correlation between pairs of measurements within subjects (interclass correlation) no larger than p=0.5], we estimate that with 44 subjects per group (88 total), we will have approximately 90% power to detect a standardized effect size of at least 0.35 (difference in comparison group means in units of standard deviation (sd)). For outcome variables having standard deviations (sd) in the range 5-15, for example, the raw effect sizes that can be detected range from approximately 2.3 to 6.9 raw units. To account for attrition during treatment (28%), and loss to followup (10-15%), we inflate the sample size accordingly to achieve a final sample size of approximately 140 subjects: 140 x 28% attrition = 101; 101 x 12% loss = 89 total participants completing all measures (note, ITT sample size will be 28% larger than power estimate requires, as treatment dropouts are included in ITT analyses).

Data Management. Charleston is the site of a VA HSRD COIN, of which [name] is an Executive Committee Member. The COIN provides all Charleston VA researchers, including [name], with VA server space, data cleaning and management services, and when requested, statistical consultation. Data entry will be by the project assistants using SPSS with range violation parameters and will follow double entry protocols (the same value must be entered twice for acceptance at two different times by two different data entry personnel for each entry). Data will be compiled using codes in lieu of personal identifiers. Access to study data will be limited to research personnel. Development of and security oversight for the electronic database for this study will be performed by study personnel trained for this purpose using a secure VA approved software to support data capture. Only de-identified case report forms will be entered into the electronic database. Thus, no protected health information (PHI) will be entered into the database. The data entry management system will be accessed and housed at the VAMC. Although no PHI will be entered into the database, data system security will be ensured by implementing multiple layered firewalls and a network intrusion prevention system for identifying and blocking malicious network activity in real time. A hard copy study log linking patient names with study ID numbers will be kept in a locked cabinet in a secure room at the VAMC, and access to this log will be limited to only key study personnel

LITERATURE CITED and RELEVANT LITERATURE:

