Study Cover Page

Official Study Title: Treatment of Prolonged Grief Disorder in Combat Veterans

NCT02283333

Protocol date: August 4, 2014

Data Analytic Plan

Baseline data were compared across groups using t-tests for continuous variables and chi-square tests for proportion variables to examine differences in demographic factors, pre-treatment symptom intensity (i.e., grief, depression, and PTSD), and co-variates that are particularly relevant to research with veterans (i.e., social support, time since death, and overall number of sessions completed). No differences in scores or proportionate representation were noted in terms of any demographic, baseline symptoms, or potential covariates. Next, repeated measures analysis of variance were conducted to determine the relative effectiveness of BATE-G vs. CT-G in terms of grief (i.e., ICG-R), depression (i.e., BDI-II) and PTSD (i.e., PCL-5) symptom outcomes. Although no covariation control (i.e., ANCOVA) was employed because covariates did not differ between groups. Baseline scores on primary dependent measures were included in the ANOVA model to test overall effects of time. The intent to treat (ITT) sample served as the primary analytic sample, and missing data were conservatively replaced through total sample mean substitution, which shares variance of missing data across groups and lessens likelihood of finding spuriously significant results. All analyses were repeated with the 'per protocol' sample, here defined as those who completed at least 5 of the 7 sessions specified in each treatment protocol. No differences in statistical significance were noted for any variable between ITT and per protocol samples, and thus the ITT sample data alone are reported.

Protocol

SIGNIFICANCE

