We will use a 2 x 4 (treatment by time) randomized controlled trial design to compare the BATE-G treatment for PGD to the VA/DoD recommended treatment for PGD: Cognitive Restructuring and Supportive Grief Counseling (from the *Iraqi War Clinician Guide, 2nd ed.*) *currently the best practices treatment advocated by VA/DoD for Veterans at Veterans Affairs Medical Center (VAMC) facilities with bereavement.* Dependent measures will include assessment of both psychological and health-related functioning at pre- treatment, post-treatment (approx 8 weeks later), and at 3 & 6 months post treatment follow up to demonstrate effectiveness of the treatment. Participants will be 140 active duty Veterans of OIF/OEF/OND or discharged Veterans of OEF/OIF/OND service who meet PGD cutoff criteria, but not criteria for PTSD, and who present for services at the VA Medical Center, Charleston. The componential BATE-G treatment (15-minute video and therapy), offered in a combined in person / televideo package, will be compared to individual Cognitive Restructuring and Supportive Grief Counseling delivered in the same number of sessions & format (a combination of in person and televideo). Participants who complete treatment and follow-up assessments will be 140 OEF/OIF/OND Veterans who meet PGD cutoff criteria outlined below. Assignment to treatment condition will be evenly distributed and randomly determined using a method identical to that of our two ongoing treatment outcome studies for PTSD in Veterans and described below.

Participants and Inclusion/Exclusion Criteria. Participants will be 140 Active Duty Service Personnel / Veterans of OIF, OEF, or OND: Participants will be male or female, age 21 and above, with PGD. Actively psychotic or demented persons, individuals with both suicidal ideation **and** clear intent, or individuals with significant homicidal ideation and or intent, and individuals meeting criteria for substance dependence will be excluded from participation; however, in order to maximize generalization of results, presence of other forms of psychopathology will not be a basis for exclusion. All structured interviews will be audiotaped to calculate inter-rater reliability on a randomly selected 20%. A 4-week medication stabilization will be required.

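### The plan does not say which term of the 2 x 4 repeated-measures ANOVA decides between the arms, and both available terms suit the question less well than one baseline-adjusted comparison of the follow-up mean

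*Combined protocol and SAP*

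**What the plan says.** Under Research Design and Methods: "We will use a 2 x 4 (treatment by time) randomized controlled trial design". The outcome visits after baseline are "post-treatment (approx 8 weeks later), and at 3 & 6 months post treatment follow up to demonstrate effectiveness of the treatment".

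The Data Analytic Plan gives the between-arm analysis in one sentence: "repeated measures analysis of variance were conducted to determine the relative effectiveness of BATE-G vs. CT-G", applied to the ICG-R, BDI-II and PCL-5. On baseline it adds: "Baseline scores on primary dependent measures were included in the ANOVA model to test overall effects of time". It also says that no covariance adjustment was used, because the covariates did not differ between groups.

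The Power Analysis describes its target as "comparing the longitudinal profile of continuous outcomes for the BATE-G versus Comparator groups across the study period". It assumes four time points, "level of significance alpha=0.05, two-tailed comparison" and "correlation between pairs of measurements within subjects (interclass correlation) no larger than p=0.5", and gives one standardized difference of 0.35.

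None of these sections says whether the treatment main effect or the treatment-by-time interaction answers the question. None names a primary visit, a planned contrast, or a between-arm estimate with a confidence interval.

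**The concern.** A 2 x 4 repeated-measures ANOVA offers two tests that involve treatment. Neither asks directly whether BATE-G patients are better after treatment.

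- **Treatment by time, 3 df.** It responds to any difference in the shape of the two profiles, lasting or transient. It has no direction and does not show at which visit the arms part. As a univariate F-test it assumes sphericity, which is doubtful when visits are unequally spaced.
- **Treatment main effect, 1 df.** It has a direction. It averages over all four visits, including baseline, where randomised arms differ only by chance. A constant post-treatment difference d therefore enters as 0.75d, and the test says nothing about timing.

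The plan's sentence about baseline concerns the overall effect of time, which is mainly a within-patient question. It leaves the between-arm test undefined. With two candidate terms, three follow-up visits and three scales, a reader cannot tell which result was meant to decide. The trial may also give up a good deal of power on data that it collects anyway.

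**Working it through.** **Inputs from the Power Analysis:** 44 per arm, effect d = 0.35 SD, two-sided alpha 0.05, correlation up to 0.5. The section's figure of 140 randomised gives 140/2 = 70 per arm for the ITT set.

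**My assumptions:** equal correlation r between all visits; arm differences of (0, d, d, d) at baseline, post-treatment, 3 and 6 months. Mean substitution for missing data is not modelled.

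**The plan's own figure.** The stated power of about 90% does not reproduce at r = 0.5. Even if the difference of 0.35 SD were present at all four visits, the test of the four-visit mean has noncentrality 22 × 0.1225/0.625 = 4.31, which is about 54% power. About 90% appears only at r = 0. The raw range of 2.3 to 6.9 units for SDs of 5 to 15 implies 0.46 SD (2.3/5 = 6.9/15 = 0.46), not 0.35. That is a separate matter. Here I use the literal inputs and compare the tests with one another.

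**Formulas and values at n = 44, d = 0.35, r = 0.5** (noncentral F, noncentrality λ):

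1. Interaction. The squared deviations of (0, d, d, d) about 0.75d sum to 0.75d². λ = (n/2) × 0.75d²/(1 − r) = 22 × 0.0919/0.5 = 4.04 on 3 and 258 df. Power 36%.
2. Main effect. λ = (n/2)(0.75d)²/[(1 + 3r)/4] = 22 × 0.0689/0.625 = 2.43 on 1 and 86 df. Power 34%.
3. Follow-up mean minus baseline. Variance (1 + 2r)/3 + 1 − 2r = 0.667; λ = 22 × 0.1225/0.667 = 4.04 on 1 and 86 df. Power 51%.
4. Follow-up mean adjusted for baseline. Variance (1 + 2r)/3 − r² = 0.417; λ = 22 × 0.1225/0.417 = 6.47 on 1 and 85 df. Power 71%.

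A simulation of 10,000 trials gave 36%, 33% and 51% for the first three tests.

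**Sustained effect of 0.35 SD, other inputs:**

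| n per arm | r | Interaction | Main effect | Change from baseline | Baseline-adjusted |
|---|---|---|---|---|---|
| 44 | 0.3 | 26% | 42% | 39% | 68% |
| 44 | 0.5 | 36% | 34% | 51% | 71% |
| 44 | 0.7 | 56% | 28% | 73% | 83% |
| 70 | 0.5 | 55% | 50% | 71% | 89% |

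**Other time patterns, 44 per arm, r = 0.5** (same formulas, with the differences at the three follow-ups as shown):

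| Differences in SD | Interaction | Main effect | Change from baseline | Baseline-adjusted |
|---|---|---|---|---|
| 0.35, 0.26, 0.175 (part fades) | 27% | 21% | 32% | 47% |
| One third, two thirds, all of 0.35 (grows) | 27% | 18% | 26% | 39% |
| 0.35, 0.175, 0 (fades fully) | 33% | 12% | 17% | 24% |

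**Why adjust rather than subtract.** The main effect and the change contrast have equal λ when 2.25/(1 + 3r) = 0.75/(1 − r), that is at r = 1/3. Below that the main effect has more power. The plan gives 0.5 as an upper limit, so lower values lie within its own range. The adjusted test has more power than both in every row above.

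**Sphericity.** In simulations with 44 per arm and correlations that decay over time (patterns I assumed), the uncorrected interaction test rejected a true null 5.5% to 6.5% of the time, against 5.1% under equal correlation.

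**The case against.** Four points on the other side have force.

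- **The plan does not adopt the interaction.** A reader might infer from the longitudinal-profile wording that the 3-df test decides, so that the trial could not say which arm did better. The documents do not support that. If the main effect is the intended test, the direction is known. The defect is that neither term is named.
- **The plan does not assume a sustained effect.** It gives one standardized difference and no time pattern. The comparator is an active therapy and follow-up runs to 6 months, so convergence is possible. If the effect fades fully, the interaction test has more power than the adjusted comparison. This stands, and limits the power claim.
- **Not every single contrast is better.** A reader might infer that any 1-df contrast clearly wins, or that the ANOVA tests have a fixed two thirds of its power. The change-from-baseline contrast loses to the main effect below correlation 1/3. The interaction-to-change ratio also moves: 0.36/0.51 is about 0.7, and 0.55/0.71 about 0.77 with 70 per arm.
- **Results are already reported.** The Data Analytic Plan states findings, so a contrast named now cannot serve as pre-specification. This stands.

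Sphericity is a small matter on these figures. Nor do the documents show that a term was picked because of its result; they only leave that question open.

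**Conclusion.** The concern holds in a limited form. The omission is plain from the text: no term, contrast or visit is named for the between-arm question. Both ANOVA tests fit that question poorly, one because it is unsigned and spread over 3 df, the other because baseline dilutes it.

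At the plan's literal inputs with a constant effect after baseline, moving to the baseline-adjusted follow-up mean raises power from about 34–36% to 71%. With 70 per arm it rises from 50–55% to 89%. These figures rest on equal correlation, no allowance for mean substitution, and a time pattern that the plan does not state. The advantage remains if the effect partly fades or grows, and reverses against the interaction test if it disappears by 6 months. The change is worth making; the plan's ANOVA is not invalid without it.

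**What to change.** For each scale, state that the deciding test is the 1-df difference between arms in the mean of the post-treatment, 3-month and 6-month scores, adjusted for that scale's baseline score rather than subtracting it, with an estimate and 95% CI. The reason for adjusting is precision, so the finding that the arms did not differ at baseline is no argument against it.

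Report the treatment-by-time test as secondary, with a Greenhouse-Geisser correction, to describe when any difference appears.

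Because analyses are already reported, say whether this contrast was pre-specified, and if not, label it so. State also which ANOVA term the reported conclusions rest on.

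The cost is a few lines of text and one further model per scale on data already collected. The statistical price is the lower power under full fading: 24% against 33% for the interaction test at correlation 0.5. The change does not settle how the three scales share the 0.05 level.

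### ANCOVA was dropped because groups were balanced at baseline, so the repeated-measures ANOVA gives up precision that the baseline scores could have supplied

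*Combined protocol and SAP*

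**What the plan says.** The Data Analytic Plan first compares the groups at baseline with t-tests and chi-square tests. It reports: "No differences in scores or proportionate representation were noted in terms of any demographic, baseline symptoms, or potential covariates". The potential covariates it lists are "social support, time since death, and overall number of sessions completed".

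The efficacy analysis follows: "repeated measures analysis of variance were conducted to determine the relative effectiveness of BATE-G vs. CT-G", for grief, depression and PTSD symptoms. Two sentences then deal with adjustment: "Although no covariation control (i.e., ANCOVA) was employed because covariates did not differ between groups", and "Baseline scores on primary dependent measures were included in the ANOVA model to test overall effects of time".

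Research Design and Methods states: "We will use a 2 x 4 (treatment by time) randomized controlled trial design". The four times are pre-treatment, post-treatment, and 3 and 6 months after treatment, so the first level of the time factor is the baseline. The Power Analysis aims at a "standardized effect size of at least 0.35" and assumes a "correlation between pairs of measurements within subjects (interclass correlation) no larger than p=0.5". No section specifies a treatment contrast adjusted for baseline, and the Data Analytic Plan does not say which ANOVA term is the efficacy test.

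**The concern.** Under randomisation, a baseline significance test looks only for a chance imbalance. It does not show whether a variable predicts outcome, and that prediction is what makes adjustment worthwhile. A perfectly balanced baseline score can still remove a large share of the residual variance.

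The sentence on ANCOVA speaks of covariates. That it also governs the outcomes' own baseline scores is a reading, supported in two ways: baseline symptoms are among the variables reported as not differing, and the only stated role of the baseline scores is to test effects of time.

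On that reading, baseline is treated as a response. The group-by-time test subtracts the whole baseline score, which is too much whenever the correlation with follow-up is below 1. A group main effect over all four visits has a different weakness: it averages in a visit at which treatment cannot yet have acted. Either way, a comparison of two active treatments, powered for a difference as small as 0.35 SD, is less sensitive than the data allow.

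A smaller point is that the number of sessions completed is listed with the covariates although it arises after randomisation. No adjustment for it was made, so no estimate is affected, but it does not belong on that list.

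**Working it through.** **Inputs.** Allocation is 1:1 (Randomization Procedures). There is one baseline and three post-baseline visits (Research Design and Methods). The Power Analysis gives two-sided alpha 0.05, within-subject correlation at most 0.5, 44 per arm, a difference of 0.35 SD, and 140 recruited, which is 70 per arm.

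**Assumptions.** The correlation ρ is the same between every pair of visits, the SD is 1 at each visit, data are complete, and the difference d is the same at the three post-baseline visits and zero at baseline.

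**The plan's own figure.** The plan states about 90% power at 44 per arm. The mean of four measurements has variance V = (1+3ρ)/4, and power is Φ(0.35·√(44/(2V)) − 1.96).
- ρ = 0: V = 0.25, power 0.907.
- ρ = 0.5: V = 0.625, power 0.546.

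The 90% therefore reproduces at ρ = 0 and not at the stated ceiling. That is a separate matter and does not decide this point, but it means there is no spare power to absorb an inefficient analysis.

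**Variance per participant at ρ = 0.5.**
- Change (post-baseline mean minus baseline): (1+2ρ)/3 + 1 − 2ρ = 0.667 + 1 − 1 = 0.667.
- Baseline-adjusted post-baseline mean: (1+2ρ)/3 − ρ² = 0.667 − 0.25 = 0.417.
- Group main effect over four visits: variance 0.625, but the effect shrinks to 0.75 × 0.35 = 0.2625. On the same scale the variance is 0.625/0.75² = 1.111.

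The ratio of adjusted to change is 0.417/0.667 = 0.625. So 88 participants analysed with adjustment give about the precision of 88/0.625 ≈ 141 without it. The ratio of adjusted to main effect is 0.417/1.111 = 0.375.

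**Power at d = 0.35, ρ = 0.5.** Noncentrality is (n/2)d²/V. At 44 per arm it is 4.04 (change) and 6.47 (adjusted); at 70 per arm, 6.43 and 10.29. The 1-df tests use the noncentral t. The 3-df tests are the group-by-time F on 3 and 3(N−2) df, and the joint adjusted test of the three visits on 3 and N−5 df.

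| Per arm | Test | Change-based | Adjusted | Relative loss |
|---|---|---|---|---|
| 44 | 1 df | 0.511 | 0.710 | 28% |
| 44 | 3 df | 0.357 | 0.531 | 33% |
| 70 | 1 df | 0.712 | 0.890 | 20% |
| 70 | 3 df | 0.545 | 0.761 | 28% |

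If the four-visit group main effect is the efficacy term, its power is 0.337 at 44 per arm and 0.496 at 70.

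A simulation of 20,000 trials gave 0.502 (change), 0.700 (adjusted) and 0.356 (interaction) at 44 per arm, and 0.708, 0.885 and 0.540 at 70. With no true effect, at 70 per arm, the rejection rates were 0.051, 0.047 and 0.049, so all three tests hold their size.

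**Sensitivity.** The loss column spans 1-df and 3-df tests at 44 and 70 per arm.

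| ρ | d | Variance ratio | Relative loss of power |
|---|---|---|---|
| 0.3 | 0.35 | 0.475 | 35–48% |
| 0.5 | 0.35 | 0.625 | 20–33% |
| 0.5 | 0.46 | 0.625 | 8–26% |
| 0.5 | 0.70 | 0.625 | at most 6% |
| 0.7 (above the plan's ceiling) | 0.35 | 0.775 | 6–16% |

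The 0.46 comes from the plan's raw differences: 2.3/5 = 6.9/15 = 0.46.

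**Effect of a chance gap.** At 70 per arm the expected absolute baseline difference is √(2/70)·√(2/π) = 0.135 SD. The change contrast moves by (1−ρ) times the gap relative to the adjusted one, here 0.5 × 0.135 ≈ 0.07 SD.

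**The case against.** The strongest reply is that a 2 x 4 repeated-measures ANOVA is valid, matches the stated design and holds its type I error, so no inference is invalid. That stands, and it limits the point to efficiency.

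Second, the ANCOVA sentence is a fragment. It may run on into the next one, with the outcome baselines as the stated exception to the lack of adjustment. This is possible. Even then, the exception gives baseline the role of testing time effects in an ANOVA, which is not adjustment of the treatment contrast.

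Third, the efficacy term is not named, so the 1-df change contrast is one candidate among several. That is fair, and it is why the 3-df interaction and the main effect are also shown. All fall short of the adjusted analysis.

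Fourth, the size depends on ρ and d. The 0.5 is a planning ceiling, not an observed correlation; the plan's raw differences imply 0.46 SD; and the pilot effect it cites is 0.7, although that pilot was uncontrolled. These considerations change the size but not the direction: adjusted variance is below change variance at every ρ below 1.

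Fifth, the complete-data figures at 70 per arm are not the planned intent-to-treat analysis, since the plan expects 89 of 140 to complete all measures and fills gaps with total-sample means. That is correct. A rough simulation of that attrition with mean substitution (d = 0.35, ρ = 0.5) gave about 0.35 against 0.66, so the advantage of adjustment does not shrink.

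**Conclusion.** The concern holds. The stated reason for omitting ANCOVA does not bear on whether adjustment is useful, and no baseline-adjusted treatment contrast is specified. At 0.35 SD and ρ = 0.5 the change-based tests lose 20–33% of the power of the adjusted ones. The loss is larger at lower correlations and small for large effects. The figures rest on exchangeable correlation, equal SDs, a constant post-baseline difference and complete data. The direction is secure. The size in this trial is not known, because the documents give neither the observed correlations nor the results. It should be corrected, but it does not make the reported tests invalid.

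**What to change.** Analyse the post-treatment, 3-month and 6-month scores with the same scale's baseline score as a covariate, regardless of baseline p-values. A constrained longitudinal model with a common baseline mean would serve equally. Name the baseline-adjusted treatment difference as the efficacy contrast. Stop using baseline significance tests to choose covariates, and take the number of sessions completed off the covariate list.

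The cost is a few lines of plan text and a re-run on data already collected. The Data Analytic Plan is written in the past tense, so if results have been seen the new analysis must be labelled post hoc and reported beside the original ANOVA.
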